## 7.2 Participant Discontinuation/Withdrawal from the Study

- A participant may discontinue from the study at any time, at his/her own request or at the discretion of the Investigator for safety, behavioral, compliance, or administrative reasons.
- At the time of study discontinuation, if possible, a discontinuation visit will be conducted, as listed in the SoA. The SoA specifies the data to collect at study discontinuation and follow-up, and any additional evaluations that need to be completed.
- If the participant revokes consent for the study, any data collected up to that point may still be used, but no future data can be generated, and any biological samples collected will be destroyed.
- A participant has the right at any time to request destruction of any biological samples taken. The investigator will document this in the site study records and the CRF and inform the Sponsor. The samples will be destroyed.
- Additional participants must be enrolled for each participant who withdraws from the study after signing consent and successfully meeting entry criteria but did not receive tepotinib and/or cetuximab. Additionally, participants excluded from the DLT analysis set may be replaced; the decision will be made by the SMC.
- The Investigator will secure the safety of the study participants and make every attempt to collect data.

## 7.3 Lost to Follow-Up

A participant will be considered lost to follow-up if he or she repeatedly fails to return for scheduled visits and is unable to be contacted by the study site.

The following actions will be taken if a participant fails to return to the clinic for a required study visit:

- The site will attempt to contact the participant and reschedule the missed visit as soon as possible, counsel the participant on the importance of maintaining the assigned visit schedule and ascertain if the participant wants to or should continue in the study.
- Before a participant is deemed “lost to follow-up”, the Investigator or designee will make every effort to regain contact with the participant: 1) where possible, make 3 telephone calls; 2) if necessary, send a certified letter (or an equivalent local method) to the participant’s last known mailing address, and 3) if a participant has given the

appropriate consent, contact the participant's general practitioner for information. These contact attempts will be documented in the participant's medical record.

- If the participant continues to be unreachable, he/she will be deemed as "lost to follow-up".

## 8

## Study Assessments and Procedures

- Study assessments and procedures and their timing are summarized in the SoA (Section 1.3). A summary of key study activities on Day 1 of Cycles 1 and 2 is provided in [Appendix 4](#).
- No protocol waivers or exemptions are allowed.
- Immediate safety concerns are discussed with the Sponsor immediately upon occurrence or awareness to determine if the participant should continue or discontinue study intervention.
- Adherence to the study design requirements, including those specified in the SoA (Section 1.3), is essential and required for study conduct.
- All screening evaluations will be completed and reviewed to confirm that potential participants meet all eligibility criteria. Laboratory tests for eligibility should be performed within 7 days prior to C1D1. The Investigator will maintain a screening log to record details of all participants screened, to confirm eligibility, and if applicable, record reasons for screening failure.
- Prior to performing any study assessments that are not part of the participant's routine medical care, the Investigator will obtain written informed consent as specified in [Appendix 2](#).
- Procedures conducted as part of the participant's routine medical care (e.g., blood count) and obtained before signing of the ICF may be used for Screening or Baseline purposes provided the procedures met the protocol-specified criteria and were performed within the time frame defined in the SoA.
- A maximum of approximately 250 mL of blood will be collected in any one-month period from each participant in the study, including any extra assessments that may be required.
- Date of birth, sex (gender), race, and ethnicity will be collected only where allowed by local law/regulations.

### 8.1

### Efficacy Assessments and Procedures

For assessment time points and procedures for primary, secondary, and [CC1](#) efficacy endpoints, see Section 1.3.

### 8.1.1 Tumor assessments

Computed tomography/magnetic resonance imaging scans will be performed and collected until disease progression is assessed by the Investigators according to RECIST Version 1.1 or start of new anti-cancer therapy. Radiographic images and physical findings (physical assessments) will be used by the Investigators for the local determination of disease progression and patient's treatment decisions. A Baseline bone scan should be performed in participants known or suspected to have bone metastases at Baseline. At Baseline, tumor lesions will be categorized in target and non-target lesions as described in RECIST Version 1.1. Results for these evaluations will be recorded with as much specificity as possible so that pre- and post-treatment results will provide the best opportunity for evaluating tumor response.

CT or MRI of the chest, abdomen, and pelvis should be conducted to evaluate disease in these locations. Imaging (preferably MRI and including T2/FLAIR) of the head at Baseline for participants who have or are suspected to have central nervous system metastases should be conducted. All lesions in the brain should be considered non-target lesions. Additional anatomic areas should be investigated in case of suspicion of presence of metastases based on signs and symptoms of individual participants. All assessments should be provided by the same physician or radiologist if possible, during the study.

For patients who are enrolled in the study and present with brain metastasis MRI assessments of brain lesions should be performed if possible. When possible, the MRI assessment shall include Coronal 3D Gd-T1WI, Axial TSE/T2WI, Axial FLAIR, Axial T1WI, and Axial Gd-T1WI.

Skeletal lesions identified at Baseline should continue to be imaged at subsequent imaging scheduled visits using localized CT, MRI, or X-ray (using the same method used at Baseline for all visits for any given lesion). After Baseline, whole body bone scans need not be repeated, unless positive at Baseline or clinically indicated.

All protocol-required images should be uploaded to the imaging repository, maintained by or on behalf of an Imaging Research Organization for a potential independent read which may be done at any appropriate time, including at the end of study or later.

Cytology results will be collected when available. Enlarging pleural/pericardial effusion and/or ascites (fluid collections) may or may not denote progression. The radiologist can utilize cytology findings (if available) to decide if significant new fluid or unequivocal and significant enlarging fluid is an indication of progression.

The Investigator may perform scans in addition to a scheduled study scan for medical reasons or if the Investigator suspects PD. Participants who withdraw from the study for clinical or symptomatic deterioration before objective documentation of PD will be requested to undergo appropriate imaging to confirm PD. Every effort should be made to confirm a clinical diagnosis of PD by imaging according to RECIST Version 1.1.

Participants will be assessed every 6 weeks starting from Cycle 3 Day 1 visit until 9 months, and every 12 weeks thereafter according to RECIST Version 1.1, until disease progression, death, withdrawal of consent, or study closure. Details on how to perform RECIST Version 1.1

assessments are provided in [Appendix 5](#). Investigator assessments will be conducted. Any CR or PR should be confirmed, preferably at the scheduled 6-week interval or at the next scheduled imaging visit, but no sooner than 4 weeks after the initial documentation of CR or PR. In the case of symptoms suggesting progression, participants should be evaluated by imaging thereafter for documentation and confirmation of the tumor responses.

The same method of assessment and the same technique should be used to characterize each identified and reported lesion at Baseline and during the study. If a chest X-ray indicates metastatic disease while the participant is enrolled in this study, a CT of the chest is required for confirmation. All assessments should be provided by the same physician or radiologist if possible during the study.

Participants who withdraw from the treatment for reasons other than progressive disease will have additional visits for tumor assessments every 6 weeks until 9 months, and every 12 weeks thereafter until disease progression. A  $\pm$  7-day time window is permitted for these additional follow-up visits until 9 months, and  $\pm$  14 days thereafter. Reasons for study termination should be recorded if this visit is the last visit for the participant. Recording of any new anticancer therapy will be made (a tumor assessment is mandatory before initiating the new therapy).

Survival Follow-up is to be performed every 3 months  $\pm$  1 month at a clinic visit or by telephone contact for up to 1-year. Participants' survival information will be collected. Any subsequent anticancer therapy given to the participant until death should be recorded.

The imaging endpoints to be assessed for efficacy evaluation according to RECIST Version 1.1 include:

- Radiographic response: best overall response (BOR), DoR, and progression-free survival (PFS) per Investigator according to RECIST Version 1.1.
- Tumor assessment during follow-up: See SoA ([Section 1.3](#)). Participants without progressive disease according to RECIST Version 1.1 at the End of Treatment Visit will be followed for disease progression according to the SoA ([Section 1.3](#)) until PD was confirmed or the maximum duration of study intervention has been reached or the study ended, whatever is reached first.

### **8.1.2 Collection and storage of images**

All study-related images will be collected by an Imaging Research Organization, then quality-checked and stored for a possible later independent review of imaging.

## **8.2 Safety Assessments and Procedures**

The safety profile of the study intervention will be assessed through the recording, reporting and analysis of Baseline medical conditions, AEs, physical examination findings, vital signs, electrocardiograms, and laboratory tests.

Comprehensive assessment of any potential toxicity experienced by each participant will be conducted starting when the participants give informed consent and throughout the study. The

Investigator will report any AEs, whether observed by the Investigator or reported by the participant; the reporting period is specified in Section 8.3.1.

Apart from the Investigator, safety data will also be assessed continuously by the Sponsor medical monitoring activities, as well as by the following committees:

- SMC during the safety run-in (refer to Section 4.1).

#### **8.2.1 Physical Examinations**

- A complete physical examination will include, at a minimum, assessments of the Cardiovascular, Respiratory, Gastrointestinal and Neurological systems. In addition, skin examination is to be performed.
- A brief physical examination will include, at a minimum, assessments of the skin, lungs, cardiovascular system and abdomen (liver).
- Investigators will pay special attention to clinical signs related to previous serious illnesses, including ILD, pancreatitis, and cardiovascular diseases.

#### **8.2.2 Vital Signs**

- Height (measured at Screening only) and weight will be measured and recorded.
- Temperature, pulse rate, respiratory rate, and blood pressure will be assessed. The method used for temperature assessment will be recorded.
- Blood pressure and pulse measurements will be assessed with a completely automated device. Manual techniques will be used only if an automated device is not available.
- Blood pressure and pulse measurements will be preceded by at least 5 minutes of rest for the participant in a quiet setting without distractions (e.g., television, cell phones).
- Vital signs will be measured preferably in a sitting position after 5 minutes rest and will include temperature, systolic and diastolic blood pressure, pulse, and respiratory rate. The participant position will be recorded.

### 8.2.3                    **Electrocardiograms**

- Triplicate 12-lead ECG will be obtained as outlined in the SoA (Section 1.3) using an ECG machine that automatically calculates the heart rate and measures PR, QRS, QT, and QTcF intervals. Participants will rest for 5 minutes in a semi-supine or supine position before the reading is taken. For study discontinuation criteria involving clinically significant QTcF findings, refer to Section 7.1.

### 8.2.4                    **Clinical Safety Laboratory Assessments**

- Blood and urine samples will be collected for the clinical laboratory tests listed in [Appendix 6](#) at the time points listed in the SoA (Section 1.3). All samples will be clearly identified.
- Additional tests may be performed at any time during the study, as determined necessary by the Investigator or required by local regulations.

The tests will be performed by local laboratories. It is required that these local laboratories are certified, perform and document interlaboratory testing at regular time intervals and provide a list of normal range laboratory values including units as defined by international system of units (SI). The Sponsor will receive a list of the local laboratory normal ranges before shipment of study intervention(s). Any changes to the ranges during the study will be forwarded to the Sponsor.

- The Investigator will review each laboratory report, document this review, and record any clinically relevant changes occurring during the study in the AE section of the eCRF. The laboratory reports will be filed with the source documents.
- Methods for sample identification during shipping and handling, as well as sampling methods, processing and storage of samples are detailed in the local Laboratory Manuals.
- Pregnancy testing (serum or highly sensitive urine, as required by local regulations) will be conducted as shown in the SoA (Section 1.3).
- Pregnancy testing (serum or highly sensitive urine, as required by local regulations) will be conducted at the end of relevant systemic exposure of the study intervention and correspond with the time frame for female participant contraception in Section 5.1.

### 8.3                            **Adverse Events and Serious Adverse Events**

- The definitions of an Adverse Event (AE) and a Serious Adverse Event (SAE) are in [Appendix 7](#).
- The Investigator and any qualified designees (e.g., Sub-Investigators) are responsible for detecting, documenting, and recording events that meet the definition of an AE or SAE. The Investigator remains responsible for following up AEs that are serious or that caused the participant to discontinue the study intervention or study, as specified in Section 8.3.3.

- Requests for follow-up will usually be made via the Study Monitor, although in exceptional circumstances the global patient safety department may contact the Investigator directly to obtain further information or to discuss the event.

### **8.3.1 Time Period and Frequency for Collecting Adverse Event and Serious Adverse Event Information**

- All SAEs will be collected from the signing of the ICF until the Safety Follow-up Visit at the time points specified in the SoA (Section 1.3). Beyond this reporting period, any new unsolicited SAEs that the Investigator spontaneously reports to the Sponsor will be collected and processed.
- All AEs will be collected from the signing of the ICF until the Safety Follow-up Visit at the time points specified in the SoA (Section 1.3).
- All SAEs will be recorded and reported to the Sponsor or designee immediately and under no circumstance will this exceed 24 hours, as indicated in [Appendix 7](#). The Investigator will submit any updated SAE data to the Sponsor within 24 hours of it being available using the same procedure that was used for the initial report.
- Investigators are not obligated to actively solicit AEs or SAEs after the end of study participation. However, if the investigator learns of any SAE, including a death, at any time after a participant has been discharged from the study, and he/she considers the event to be reasonably related to the study intervention or study participation, the Investigator will promptly notify the Sponsor.

### **8.3.2 Method of Detecting Adverse Events and Serious Adverse Events**

At each study visit, the participant will be queried on changes in his or her condition.

Care will be taken not to introduce bias when detecting AEs and/or SAEs. Open-ended and non-leading verbal questioning of the participant is the preferred method to inquire about AE occurrences.

The method of recording, evaluating, and assessing causality of AEs and SAEs and the procedures for completing and transmitting SAE reports are in [Appendix 7](#). All SAEs and all nonserious AEs of special interest (AESI) (see Section 8.3.7) must be additionally documented and reported using the appropriate Report Form as specified in [Appendix 7](#).

### **8.3.3 Follow-up of Adverse Events and Serious Adverse Events**

After the initial AE/SAE report, the Investigator is required to proactively follow each participant at subsequent visits/contacts. All SAEs and AESIs (as defined in Section 8.3.7) will be followed until resolution, stabilization, the event is otherwise explained, or the participant is lost to follow-up (as defined in Section 7.3). No new information is expected. Reasonable attempts to obtain this information will be made and documented. It is also the Investigator's responsibility to ensure that

any necessary additional therapeutic measures and follow-up procedures are performed. Further information on follow-up procedures is in [Appendix 7](#).

### **8.3.4 Regulatory Reporting Requirements for Serious Adverse Events**

Prompt notification by the Investigator to the Sponsor of an SAE (particularly life-threatening and deaths) is essential so that legal obligations and ethical responsibilities towards the safety of participants and the safety of a study intervention under clinical investigation are met.

The Sponsor has a legal responsibility to notify both the local regulatory authority and other regulatory agencies about the safety of a study intervention under clinical investigation. The Sponsor will comply with country-specific regulatory requirements relating to safety reporting to the regulatory authority, Institutional Review Boards (IRB)/Independent Ethics Committees (IEC), and Investigators.

Individual Case Safety Reports will be prepared for suspected unexpected serious adverse reactions (SUSAR) according to local regulatory requirements and Sponsor policy and forwarded to Investigators, as necessary.

An Investigator who receives an Individual Case Safety Report describing a SUSAR or other specific safety information (e.g., Emerging Safety Issue Report, summary or listing of SAEs/SUSARs) from the Sponsor will review and then file it along with the Investigator Brochure in the Investigator's Site File and will notify the IRB/IEC, if appropriate according to local requirements.

In this global clinical multicenter study, the Sponsor is in the best position to determine an unanticipated problem (as defined in US Regulations 21 CFR 312.66). The Sponsor will immediately notify all Investigators of findings that could adversely affect the safety of participants, impact the conduct of the study or alter the IRB's approval/favorable opinion to continue the study. An unanticipated problem is a serious adverse event that by its nature, incidence, severity, or outcome has not been identified in the current version of the risk analysis report, specified in Section [2.3](#).

AESIs specified in Section [8.3.7](#) will be reported to the Sponsor (or delegate) in an expedited manner as described in [Appendix 7](#).

### **8.3.5 Pregnancy**

- Details of all pregnancies in female participants and, female partners of male participants will be collected after the start of study intervention and until the Safety Follow-up Visit.
- If a pregnancy is reported, the Investigator will inform the Sponsor within 24 hours of learning of the pregnancy and will follow the procedures specified below for collection of pregnancy information.
- Abnormal pregnancy outcomes (e.g., spontaneous abortion, fetal death, stillbirth, congenital anomalies, ectopic pregnancy) are considered SAEs.

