## Follow-up Period

All participants are to be followed up after stop of treatment with tepotinib and cetuximab, including an End of Treatment (EoT) Visit within 14 days of the last dose of tepotinib and/or cetuximab. A Safety Follow-up Visit will occur 30 (- 3 to + 7) days after the last dose of tepotinib and/or cetuximab for all participants who discontinued the study intervention permanently. After the Safety Follow-up Visit, the Survival Follow-up is to be performed every 3 months ( $\pm$ 1 month) at clinic visits or by telephone contact for up to 1 year. Participants' survival information will be collected. Any subsequent anticancer therapy given to the participant until death should be recorded.

Participants who discontinue treatment for reasons other than progressive disease (PD) or death will have additional visits for tumor assessments every 6 weeks until 9 months and every 12 weeks thereafter until disease progression, death, or withdrawal of consent. A  $\pm$  7-day time window is permitted for these additional follow-up visits until 9 months, and  $\pm$  14 days thereafter.

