## Sex

12. Are male or female

Contraceptive use by males or females will be consistent with local regulations on contraception methods for those participating in clinical studies.

a. Male Participants:

Agree to the following during the study intervention period and for at least 4 months after the last dose of study intervention:

- Refrain from donating sperm

PLUS, either:

- Abstain from intercourse with a woman of child bearing potential

OR

- Use a male condom:
  - When having sexual intercourse with a woman of child bearing potential, who is **not** currently pregnant, **and** advise her to use a highly effective contraceptive method with a failure rate of <1% per year, as described in [Appendix 3](#), since a condom may break or leak.

b. Female Participants:

- Are **not** pregnant or breastfeeding, and at least one of the following conditions applies:
  - **Not** a woman of child bearing potential

OR

- If a woman of child bearing potential, use a highly effective contraceptive method (i.e., with a failure rate of <1% per year), preferably with low user dependency, as described in [Appendix 3](#) for the following time periods:
  - Before the first dose of the study intervention(s), if using hormonal contraception:
    - Has completed at least one 4-week cycle of an oral contraception pill and either had or has begun her menses

OR

- Has used a depot contraceptive or extended-cycle oral contraceptive for least 28 days and has a documented negative pregnancy test using a highly sensitive assay.

AND

A barrier method, as described in [Appendix 3](#).

- During the intervention period
- After the study intervention period (i.e., after the last dose of study intervention is administered) for at least 2 months after the last dose of study intervention and agree not to donate eggs (ova, oocytes) for reproduction during this period.
- The investigator evaluates the effectiveness of the contraceptive method in relationship to the first dose of study intervention.
- Have a negative serum or highly sensitive urine pregnancy test, as required by local regulations, within 24 hours before the first dose of study intervention. If a urine test cannot be confirmed as negative (e.g., an ambiguous result), a serum pregnancy test is required.
- Additional requirements for pregnancy testing during and after study intervention are in Section [8.2.4](#).

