#### Embryo-fetal Toxicity

Tepotinib can cause fetal harm when administered to pregnant women.

Women of childbearing potential or male participants with female partners of childbearing potential should be advised of the potential risk to a fetus.

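### Protocol 8.3.5 gives two conflicting windows for collecting pregnancies, and the shorter one ends before the protocol's own contraception periods; 8.2.4 and the Schedule of Activities likewise disagree on the last pregnancy test

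*Protocol*

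**What the plan says.** **Collection window, narrow wording.** The first bullet of Protocol 8.3.5 says that details of pregnancies in female participants and in partners of male participants "will be collected after the start of study intervention and until the Safety Follow-up Visit". Section 4.1 (Follow-up Period) fixes that visit: "A Safety Follow-up Visit will occur 30 (- 3 to + 7) days after the last dose of tepotinib and/or cetuximab".

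**Collection window, wide wording.** The paragraphs on collecting pregnancy information, further down in 8.3.5, use a different limit. The investigator collects information on any female participant who becomes pregnant during her time on study and follows her for outcome. The investigator also attempts to do so for a partner who becomes pregnant during the male participant's time on study. Section 4.4 treats a participant as having completed the study only after Survival Follow-up, which lasts up to 1 year.

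**Contraception.** Section 5.1, criterion 12, requires contraception from women of childbearing potential "for at least 2 months after the last dose of study intervention" and from men "for at least 4 months after the last dose of study intervention". Section 6.5.4.2 gives the background: "Tepotinib can cause fetal harm when administered to pregnant women".

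**Testing.** Section 5.1 refers to 8.2.4 for pregnancy tests during and after treatment. Section 8.2.4 calls for a test at the end of relevant systemic exposure, which is to "correspond with the time frame for female participant contraception in Section 5.1". In the Schedule of Activities (Section 1.3) the last pregnancy test is at the Safety Follow-up Visit, and the survival follow-up column is empty for that row.

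**The concern.** A site needs one answer to a simple question: until when do I record a pregnancy? Section 8.3.5 gives two. The first bullet is the only sentence with an explicit start and stop. It also introduces the procedures that follow, so a site could reasonably read it as the rule and the later paragraphs as instructions for cases already within it.

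The visit schedule supports that narrow reading. Survival contacts are described in Sections 4.1 and 8.1.1 as collecting survival status and subsequent anticancer therapy, and neither section mentions pregnancy. Routine collection of adverse events and serious adverse events also stops at the Safety Follow-up Visit (Section 8.3.1), although 8.3.5 classes spontaneous abortion and stillbirth as always serious.

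What is at stake is safety capture. A pregnancy that starts after the 30-day visit but within the required contraception period may not be asked about, for a drug that the protocol says can harm a fetus. With at most 48 treated participants, such events should be rare, but each would be an individual safety report.

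**Working it through.** The plan states no figure to reproduce here. The check compares time windows after the last dose.

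**Inputs**
- Safety Follow-up Visit: day 30, window day 27 to day 37 (Protocol 4.1 and Schedule of Activities).
- Contraception after last dose: at least 2 months for women, at least 4 months for men (Protocol 5.1).
- 1 month = 30.4375 days (SAP 9.5). The protocol does not define a month for contraception, so using this factor is an assumption.
- Survival contacts: every 3 months, ± 1 month, after the Safety Follow-up Visit, for up to 1 year (Protocol 4.1).

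**Step 1: gap under the narrow wording**

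Gap = contraception months × 30.4375 − day of Safety Follow-up Visit.

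| | Contraception period | Visit day 27 | Visit day 30 | Visit day 37 |
|---|---|---|---|---|
| Women | 2 × 30.4375 = 60.9 days | 33.9 days (56%) | 30.9 days (51%) | 23.9 days (39%) |
| Men | 4 × 30.4375 = 121.8 days | 94.8 days (78%) | 91.8 days (75%) | 84.8 days (70%) |

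Percentages are shares of the contraception period. Because both periods are stated as minimums, the gaps are minimums too.

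**Step 2: gap under the wide wording**

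If being on study includes Survival Follow-up, a full year of it ends near day 30 + 12 × 30.4375 = 395. That is beyond both 60.9 and 121.8 days, so the uncovered time is 0 days for women and men. This requires that the participant stays in follow-up and that the sponsor does not end the study early; in the latter case Section 4.4 drops the 1-year follow-up.

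The two readings of one section therefore differ by about 31 days (women) and 92 days (men) of the contraception period.

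**Step 3: could the planned contacts cover the period?**

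Counting the 3-month interval from the Safety Follow-up Visit:
- Nominal first contact: 30 + 3 × 30.4375 = day 121.3.
- Earliest: 27 + 2 × 30.4375 = day 87.9.
- Latest: 37 + 4 × 30.4375 = day 158.8.

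For women, even the earliest first contact falls after day 60.9, so one question at that contact covers the period. For men, the nominal first contact (day 121.3) falls just short of day 121.75, and the earliest is about a month short. Some men would need the question again at the second contact, nominally 30 + 6 × 30.4375 = day 212.6.

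**Step 4: testing**

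The test in 8.2.4 is linked to the female contraception period, about day 61. The last scheduled test is at day 27 to 37. A site that follows the Schedule alone does not meet 8.2.4.

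**The case against.** A reader who stops at the first bullet might infer that pregnancies arising after the 30-day visit would simply go uncollected and unfollowed. The documents do not support that. The later paragraphs of 8.3.5 require collection and outcome follow-up for female participants on study, and an attempt at both for partners. Other routes also stay open. A reported pregnancy goes to the sponsor within 24 hours, with no end date given for that duty. Abnormal outcomes are serious adverse events. Unsolicited serious events reported after the collection period are still processed (Section 8.3.1). Post-study pregnancy-related serious events judged related must be reported. This part of the objection stands: late cases are nominally covered.

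A reader might also treat the contraception periods as the protocol's stated period of fetal risk. That goes further than the text. Section 6.5.4.2 gives no duration. Section 8.2.4 links the female period to systemic exposure, but no such link is given for men. For men, where the gap is larger, the step from contraception period to risk period is an inference.

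On testing, the requirement does exist in 8.2.4, so what remains is a mismatch between text and table.

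None of this removes the contradiction. The wide wording has no visit, question or form at survival contacts to put it into practice. It lapses if the sponsor ends the study early. The remaining routes depend on someone volunteering the information.

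**Conclusion.** Wrong as written, minor severity. Section 8.3.5 sets two incompatible collection windows. The shorter one ends about 31 days (range 24 to 34) before the minimum contraception period for women and about 92 days (range 85 to 95) before that for men. Section 8.2.4 and the Schedule of Activities disagree on whether a pregnancy test follows the 30-day visit.

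The supported conclusion is that a site following the first bullet and the Schedule could miss late pregnancies. It is not that the protocol as a whole leaves them unreported, nor that it states a fetal-risk period of a given length.

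The sizes rest on the SAP's month length and on the stated visit window. The zero gap under the wide wording rests on reading Survival Follow-up as time on study, as Section 4.4 does. Sample size, endpoints and efficacy results are unaffected.

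**What to change.** - **Section 8.3.5:** reconcile the first bullet with the later paragraphs so that one collection window applies to female participants and one to partners, neither shorter than the contraception periods already in Section 5.1. Say what happens to participants still inside that window if the study is ended early.
- **Survival contacts (Sections 1.3, 4.1 and 8.1.1):** add a pregnancy question, asked up to and including the first contact after the relevant contraception period ends. That is the first contact for women and, depending on timing, the first or second for men.
- **Section 8.2.4 and the Schedule of Activities:** reconcile the text with the pregnancy-test row. Survival contacts may be by telephone, so if a later test is meant, the Schedule must say how it is obtained. Which passage is right is for the sponsor to settle.

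**Cost:** a wording amendment and one extra question at contacts already planned. Any late partner case would also need the partner's signed consent and outcome follow-up, generally to no later than 6 to 8 weeks after the estimated delivery date under 8.3.5. Few such cases are expected. No change to the analysis is needed.
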